14.3. Analysis Populations

Safety Population:

All subjects who were administered any test article excluding subjects who drop out prior to administering any test article. At least one observation should be recorded.

Per-Protocol Population:

All subjects who have successfully completed all assessments and did not substantially deviate from the protocol as determined by the trial cohort review committee prior to database hard lock (Per-Protocol Population). Justification of excluding subjects with protocol deviations in the per-protocol population set will be documented in a memo to file.

14.4. Level of Statistical Significance

All planned analysis for this study will be conducted with an overall type I error rate of 5%. No adjustment for multiple comparisons will be conducted unless specified otherwise.

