14.5. Primary Analysis

All analyses will be conducted on the analysis population (defined above). If the difference between the analysis and safety populations is higher than 15% then a sensitivity analysis will be conducted on all available data.

Primary Endpoints – Overall Fit Acceptance: Overall lens fit acceptability will be analysed using a generalised linear mixed model with a multinomial distribution and a cumulative logit link function. Sequence of lens wear, base curve, period, lens type, site, and the two-way interactions between lens type and base curve and between lens type and period will be included in each model as fixed effects. An appropriate covariance structure will be used to model the residual errors between measurements within same subject across study periods. The covariance structure will be selected based on the finite-sample corrected Akaike’s Information Criterion. Covariance structures considered include:

- Unstructured Covariance Structure (UN)
- Homogenous Compound symmetry (CS)

The Kenward and Roger method⁴ will be used for the denominator degree of freedom. If convergence is problematic, then reduced versions of the above model may be considered.

Comparisons between the Test lens and the control lens will be carried out using two-sided 95% confidence intervals constructed for odds ratio (Test/Control) by base curve. The lower limits of the 95% confidence intervals will be compared to 1.6 and 1 to Test for non-inferiority and superiority, respectively. Non-inferiority of the Test lens relative to the control will be concluded if the upper limit is below 1.6. The superiority will be established if the upper limit is below 1.

Primary Endpoints – Lens Power Requirement: The difference in lens power requirement between the Test and Control lenses will be calculated by base curve for the purpose of the analyses. The proportions, and the corresponding 95% confidence intervals, of eyes with no difference in lens power requirement and with a difference within ± 0.25 D will be calculated. The 95% two-sided confidence intervals of the proportions will be calculated using the method of Wilson.³ The lower limits of the confidence intervals will be compared to 70% and 80%. Equivalence will be established if the lower limit of the proportion with no differences is above 70% and if the lower limit of the proportion within ± 0.25 D is above 80%.

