14.6. Secondary Analysis

Secondary Endpoints – Comfort and Handling: The subjective ratings of comfort and handle ability will be analysed using a linear mixed model. Sequence of lens wear, base curve, period, lens type, site, and the two-way interactions between lens type and base curve and between lens type and period will be included in each model as fixed effects. An appropriate covariance structure will be used to model the residual errors between measurements within same subject across study periods. The covariance structure will be selected based on the finite-sample corrected Akaike's Information Criterion. Covariance structures considered include:

- Unstructured Covariance Structure (UN)
- Homogenous Compound symmetry (CS)

The Kenward and Roger method⁴ will be used for the denominator degree of freedom. If convergence is problematic, then reduced versions of the above model may be considered.

Comparisons between the Test lens and the Control lens will be carried out using two-sided 95% confidence intervals constructed for least-square mean differences (Test minus Control) separately for each base curve. The lower limits of the 95% confidence intervals will be compared to -1 and 0 to Test for non-inferiority and superiority, respectively. Non-inferiority of the Test lens relative to the Control will be concluded if the lower limit is above -1. The superiority will be established if the lower limit is above 0.

Secondary Endpoints – Vision Quality: The subjective rating of vision quality will be analysed using a linear mixed model. Sequence of lens wear, base curve, period, lens type, site, and the two-way interactions between lens type and base curve and between lens type and period will be included in each model as fixed effects. An appropriate covariance structure will be used to model the residual errors between measurements within same subject across study periods. The covariance structure will be selected based on the finite-sample corrected Akaike's Information Criterion. Covariance structures considered include:

- Unstructured Covariance Structure (UN)

- Homogenous Compound symmetry (CS)

The Kenward and Roger method⁴ will be used for the denominator degree of freedom. If convergence is problematic, then reduced versions of the above model may be considered.

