Comparisons between the Test lens and the Control lens will be carried out using two-sided 95% confidence intervals constructed for least-square mean differences (Test minus Control) separately for each base curve. The lower limits of the 95% confidence intervals will be compared to -10 and 0 to Test for non-inferiority and superiority, respectively. Non-inferiority of the Test lens relative to the Control will be concluded if the lower limit is above -10. The superiority will be established if the lower limit is above 0.

Secondary Endpoints – High Contrast Visual Acuity: Monocular high contrast VA scores will be analysed using a linear mixed model. Sequence of lens wear, base curve, period, lens type, site, and the two-way interactions between lens type and base curve and between lens type and period will be included in each model as fixed effects. An appropriate covariance structure will be used to model the residual errors between measurements within same subject eye across study periods. The covariance structure will be selected based on the finite-sample corrected Akaike's Information Criterion. Covariance structures considered include:

- Unstructured Covariance Structure (UN)
- Homogenous Compound symmetry (CS)

The Kenward and Roger method⁴ will be used for the denominator degree of freedom. If convergence is problematic, then reduced versions of the above model may be considered.

Comparisons between the Test lens and the Control lens will be carried out using two-sided 95% confidence intervals constructed for least-square mean differences (Test minus Control) separately for each base curve. The upper limits of the 95% confidence intervals will be compared to 0.1 and 0 logMAR to Test for non-inferiority and superiority, respectively. Non-inferiority of the Test lens relative to the Control will be concluded if the upper limit is below 0.10 logMAR. The superiority will be established if the upper limit is below 0.00 logMAR.

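### The overall 5% type I error that section 14.4 claims for all planned analysis is really the two-sided error of each unadjusted 95% interval; the primary objective is essentially protected, the secondary claims are not

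*Combined protocol and SAP*

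**What the plan says.** Section 14.4 says that all planned analysis "will be conducted with an overall type I error rate of 5%. No adjustment for multiple comparisons will be conducted unless specified otherwise". No visible text in 14.5 or 14.6 specifies an adjustment, a testing order or a gate from primary to secondary endpoints.

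- **Fit (14.5):** "two-sided 95% confidence intervals constructed for odds ratio (Test/Control) by base curve". The bounds are 1.6 for non-inferiority and 1 for superiority.
- **Lens power (14.5):** the Test–Control difference "will be calculated by base curve for the purpose of the analyses". Equivalence has two conditions, introduced as "if the lower limit of the proportion with no differences is above 70% and if the lower limit of the proportion within"; the second threshold, for agreement to a quarter dioptre, is 80%. Both criteria are needed.
- **Comfort, handling, vision quality and high contrast acuity (14.6):** 95% intervals for "least-square mean differences (Test minus Control) separately for each base curve", each read against a non-inferiority margin and against zero. For the three subjective ratings, "The superiority will be established if the lower limit is above 0". For acuity, "The upper limits of the 95% confidence intervals will be compared to 0.1 and 0 logMAR to Test for non-inferiority and superiority, respectively".

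Section 2.3 makes the study's objectives depend on meeting both primary hypotheses. It lists the four secondary endpoints as formal hypotheses with margins. Most hypotheses there compare lenses of similar base curve, but no visible text says whether one or both base curves must pass. Part of 14.2 is redacted.

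**The concern.** The two sentences of 14.4 cannot both hold for every planned analysis. An overall 5% across several separate claims needs an adjustment, an ordering, or a rule that all must succeed. The plan has such a rule only for the primary objective.

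The secondary results are where this matters. The synopsis classes the study as post-marketing, for marketing claims, and 14.6 declares superiority from a single unadjusted limit. A reader who relies on 14.4 would credit any one of those findings with an overall 5% guarantee that it does not have. The null case for superiority is not remote: it is that two lenses which the protocol itself describes as similar do not differ.

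**Working it through.** **Inputs from the documents.** Two-sided 95% intervals; one limit decides each secondary claim; two base curves; four secondary endpoints, hence 4 × 2 = 8 secondary comparisons (comfort counted once, although section 7.1 records it on insertion and on settling); at least 43 completers (4.3) and up to 60 enrolled. **Assumed:** the correlation ρ between test statistics, which the documents do not give; 0, 0.5, 0.75 and 0.9 are used.

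**1. Reproducing the stated 5%.** 2 × (1 − Φ(1.96)) = 0.05, or 0.025 per limit. The figure reproduces as the two-sided error of one interval and not as an overall rate.

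**2. Primary objective.** Both hypotheses are required, so the error is at most that of whichever one is false.
- Both base curves required: nominally at most 2.5%.
- Either base curve sufficient: at most 1 − 0.975² = 4.94% if the curves are independent.
- The Wilson rule for lens power is discrete. Against 70%, a pass needs 36 of 43, with exact error 3.11% per curve; either curve, independent: 1 − (1 − 0.0311)² = 6.1%. With 60 completers it needs 49, with error 2.95%; either curve: 5.8%. Against 80%, a pass needs 40 of 43 (error 1.78%), or 3.5% for either curve. The excess over 5% comes from discreteness.

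**3. Secondary endpoints, each base curve its own claim.** The chance of at least one false claim among k true nulls, at one-sided 2.5% with equal correlation, is

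P = 1 − ∫ φ(g) · Φ((1.96 − √ρ·g)/√(1−ρ))^k dg, which is 1 − 0.975^k at ρ = 0.

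| k | ρ = 0 | 0.5 | 0.75 | 0.9 |
|---|---|---|---|---|
| 2 | 4.94% | 4.54% | 4.05% | 3.52% |
| 3 | 7.31% | 6.27% | 5.20% | 4.18% |
| 4 | 9.63% | 7.79% | 6.13% | 4.68% |
| 5 | 11.89% | 9.15% | 6.91% | 5.08% |
| 8 | 18.33% | 12.52% | 8.73% | 5.95% |

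- *Superiority:* if the lenses do not differ, all eight nulls are true and the last row applies.
- *Non-inferiority:* k is the number of comparisons whose true difference sits exactly at its margin. The last row is the extreme. The rate passes 5% from k = 3 at correlations up to 0.75, and from k = 5 at 0.9.

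**4. Secondary endpoints, both base curves required.**
- *Superiority:* the error per endpoint is 2 × 0.025 minus the k = 2 value, which gives 0.06%, 0.46%, 0.95% and 1.48%, with ρ now the correlation between the two curves. Over four endpoints treated as independent of each other, 1 − (1 − p)⁴ gives 0.25%, 1.84%, 3.75% and 5.80%.
- *Non-inferiority:* the worst case per endpoint is 2.5%, with one curve at the margin and the other well inside it. The four-endpoint worst case is the k = 4 row: 9.6%, 7.8%, 6.1% and 4.7%.

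**The case against.** The strongest defence is that 14.4 hides nothing. It sits under a heading about significance level and says outright that no adjustment is made, so many readers would take 5% as the level of each interval. Leaving separately stated secondary hypotheses unadjusted, with disclosure, is a legitimate choice, and the study's success rule does not depend on them. The size of the problem also turns on an unstated rule: if each endpoint needs both curves, the superiority error is below 5% except at very high between-curve correlation. The non-inferiority figures need several true differences to sit at their margins at once.

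Most of this stands, and it limits the weight of the point. It does not rescue the words that claim an overall rate for all planned analysis. The wording of 14.6, separate by base curve, favours the per-curve reading, and exploratory work has its own section (14.7), so the secondaries are not presented as exploratory.

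Stronger readings that a reader might infer, and that the documents do not support:
- *The primary conclusion is inflated by multiplicity.* Section 2.3 requires both primary hypotheses.
- *There is a 22.4% chance of a false superiority claim, from ten independent tests.* That count includes fit, where 14.5 says "The lower limits of the 95% confidence intervals will be compared to 1.6 and 1 to Test for non-inferiority and superiority" but then decides on the upper limit. With both limits named, fit does not supply a clear superiority test to count.
- *Each decision carries a full 5% (33.7% over eight).* Each secondary decision uses one limit, at 2.5%.
- *Non-inferiority and superiority errors add up.* For any one comparison the two nulls exclude each other: lenses that do not differ cannot yield a false non-inferiority claim.

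**Conclusion.** The concern holds as a misstatement of error control. The 5% in 14.4 is a per-interval rate. The primary objective is kept at or near 5% on either base-curve reading; the one excess is the lens power rule under an either-curve reading, up to 6.1% with 43 completers and 5.8% with 60 if the curves are independent.

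For the secondary endpoints the overall claim is not met in general. On the per-curve reading the false superiority rate exceeds 5% at every correlation examined. On the both-curve reading it mostly does not, while worst-case non-inferiority still does up to a correlation of 0.75. All these sizes rest on assumed, equal correlations and, for the both-curve superiority figures, on independence between endpoints. That the stated overall rate is not delivered does not depend on any particular correlation value: no procedure in the visible text would secure it.

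**What to change.** In 14.4, limit the overall 5% statement to the primary objective. Add that secondary and superiority intervals are unadjusted, each at a per-comparison two-sided 5% (2.5% per limit), and that superiority findings are reported as not controlled for multiplicity. This is a wording change with no effect on sample size or conduct. Its cost is that secondary and superiority results carry less weight.

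As a clarification only, state in 2.3 and 14.5–14.6, before database lock, whether one or both base curves must pass for each endpoint. The choice is the sponsor's. Requiring both needs no alpha adjustment for the primary objective but lowers power; accepting either brings the primary error to the levels in step 2 of the working.

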14.5. Primary Analysis

All analyses will be conducted on the analysis population (defined above). If the difference between the analysis and safety populations is higher than 15% then a sensitivity analysis will be conducted on all available data.

Primary Endpoints – Overall Fit Acceptance: Overall lens fit acceptability will be analysed using a generalised linear mixed model with a multinomial distribution and a cumulative logit link function. Sequence of lens wear, base curve, period, lens type, site, and the two-way interactions between lens type and base curve and between lens type and period will be included in each model as fixed effects. An appropriate covariance structure will be used to model the residual errors between measurements within same subject across study periods. The covariance structure will be selected based on the finite-sample corrected Akaike’s Information Criterion. Covariance structures considered include:

- Unstructured Covariance Structure (UN)
- Homogenous Compound symmetry (CS)

The Kenward and Roger method⁴ will be used for the denominator degree of freedom. If convergence is problematic, then reduced versions of the above model may be considered.

Comparisons between the Test lens and the control lens will be carried out using two-sided 95% confidence intervals constructed for odds ratio (Test/Control) by base curve. The lower limits of the 95% confidence intervals will be compared to 1.6 and 1 to Test for non-inferiority and superiority, respectively. Non-inferiority of the Test lens relative to the control will be concluded if the upper limit is below 1.6. The superiority will be established if the upper limit is below 1.

Primary Endpoints – Lens Power Requirement: The difference in lens power requirement between the Test and Control lenses will be calculated by base curve for the purpose of the analyses. The proportions, and the corresponding 95% confidence intervals, of eyes with no difference in lens power requirement and with a difference within ± 0.25 D will be calculated. The 95% two-sided confidence intervals of the proportions will be calculated using the method of Wilson.³ The lower limits of the confidence intervals will be compared to 70% and 80%. Equivalence will be established if the lower limit of the proportion with no differences is above 70% and if the lower limit of the proportion within ± 0.25 D is above 80%.

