2.2. Endpoints

Primary Efficacy Endpoints

The primary endpoints are overall lens fit acceptability and lens power requirement.

Overall lens fit acceptability will be graded by the investigator on a 0-5 scale (VCR grading scale, where 5 indicates a perfect fit) and will be based on fitting characteristics such as centration and movement (not comfort or vision).

The proportion of subjects with similar (± 0.00 D and ± 0.25 D) lens power requirements for each lens type will be calculated. The lens requirements will be calculated from the lens power and spherical over-refraction by summing the lens power and the over-refraction.

Secondary Endpoints

The secondary endpoints are subjective ratings of comfort, vision quality and handling as well as high contrast visual acuity.

Comfort and handling will be scored by the subject on an 11-point scale (0-10).

Vision quality will be scored by the subject on a 0-100 scale.

High contrast visual acuity will be recorded with contact lenses only using logMAR charts.

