2.3. Hypotheses

Both primary hypotheses must be met in order to satisfy the objectives of this study.

Primary Study Hypotheses	
1	The overall fit acceptance of ACUVUE® OASYS 1·Day will be non-inferior to that of 1·Day ACUVUE® TruEye® of similar base curve. A non-inferiority bound of 1.6 will be used for the odds ratio.
2	The lens power requirement for ACUVUE® OASYS 1·Day will be the same as that of 1·Day ACUVUE® TruEye® in at least 70% of cases and within ± 0.25 D for at least 80% of cases.
Secondary Study Hypotheses	
1	The short-term comfort of ACUVUE® OASYS 1·Day will be non-inferior to that of 1·Day ACUVUE® TruEye® of similar base curve. A non-inferiority bound of 1.0 (0-10 scale) will be used.
2	The subjective vision quality of ACUVUE® OASYS 1·Day will be non-inferior to that of 1·Day ACUVUE® TruEye® of similar base curve. A non-inferiority bound of 10 (0-100 scale) will be used.
3	Monocular high contrast visual acuity with ACUVUE® OASYS 1·Day will be non-inferior to that of 1·Day ACUVUE® TruEye® of similar base curve. A non-inferiority bound of 0.1 logMAR will be used.
4	The handling performance of ACUVUE® OASYS 1·Day will be non-inferior to that of 1·Day ACUVUE® TruEye® of similar base curve. A non-inferiority bound of 1 (0-10 scale) will be used.

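### The co-primary lens-fit rule names the lower confidence limit once and the upper limit twice, and does not say which way the odds ratio runs

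*Combined protocol and SAP*

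**What the plan says.** Section 2.2 has the investigator grade overall fit on a "0-5 scale (VCR grading scale, where 5 indicates a perfect fit", so a higher grade is better. Section 2.3 makes fit the first of two primary hypotheses, requires both to succeed, and gives the margin without a direction: "A non-inferiority bound of 1.6 will be used for the odds ratio".

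Section 14.5 fits a cumulative logit mixed model and compares the lenses through "two-sided 95% confidence intervals constructed for odds ratio (Test/Control) by base curve". Three sentences on the decision follow:

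1. "The lower limits of the 95% confidence intervals will be compared to 1.6 and 1 to Test for non-inferiority and superiority, respectively".
2. "Non-inferiority of the Test lens relative to the control will be concluded if the upper limit is below 1.6".
3. "The superiority will be established if the upper limit is below 1".

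Sentence 1 names the lower limit; sentences 2 and 3 name the upper limit. The odds ratio is described only as Test over Control. Neither section says whether the odds are of a higher or a lower grade, or in which order the model accumulates the categories.

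**The concern.** There are two gaps. The rule refers to both ends of the interval, and a non-inferiority decision needs one. Also, a cumulative logit can be built toward higher or lower grades, and switching between them inverts the odds ratio. A margin of 1.6 with an upper-limit criterion makes sense for one of those directions and is backwards for the other.

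The study cannot succeed without this endpoint. As the text stands, the direction of the odds has to be worked out by inference, and nothing in writing prevents it from being settled after the data are in hand. The endpoint is named for acceptance or acceptability, so an analyst could naturally model the odds of a good fit. With that coding, the written criteria would reward a worse lens.

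**Working it through.** **Comparison with the other endpoints (Section 14.6)**

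| Endpoint | Better direction | Limit in the comparison sentence | Limit in the conclusion sentences |
|---|---|---|---|
| Comfort, handling | higher | lower | lower |
| Vision quality | higher | lower | lower |
| High contrast acuity (logMAR) | lower | upper | upper |
| Overall fit (Section 14.5) | higher grade | **lower** | **upper** |

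Every secondary endpoint uses one limit throughout. The comfort and handling text reads "The lower limits of the 95% confidence intervals will be compared to -1 and 0 to Test for non-inferiority and superiority, respectively", the same sentence as the fit one apart from the numbers. The acuity text reads "Non-inferiority of the Test lens relative to the Control will be concluded if the upper limit is below 0.10 logMAR", the form used in the fit conclusions. The fit paragraph looks like a join of the two templates.

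**Inputs**

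- Margin 1.6 and two-sided 95% interval: Sections 2.3 and 14.5.
- Standard error (SE) of the log odds ratio: not given in the documents, so assumed. A proportional-odds approximation is Var = 12 / [2n(1 − Σp³)] × (1 − ρ), with n = 43 completers per base curve (Section 4.3) and Σp³ = 0.2 (assumed).
  - ρ = 0: Var = 12 / (86 × 0.8) = 0.174, SE = 0.418.
  - ρ = 0.5 (the correlation in Section 14.2, stated there for clustered binary data): Var = 0.087, SE = 0.295.
  - Range used for the intervals: 0.29 to 0.42.

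**Intervals: exp(ln OR ± 1.96 × SE)**

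| Estimate | 95% CI, SE 0.29 | 95% CI, SE 0.42 | Result of the upper-limit rule |
|---|---|---|---|
| *Odds of a better grade* | | | |
| OR 0.40 (Test worse) | 0.23 to 0.71 | 0.18 to 0.91 | superior |
| OR 2.0 (Test better) | 1.13 to 3.53 | 0.88 to 4.56 | not non-inferior |
| *Same lenses, odds of a worse grade* | | | |
| OR 2.5 (= 1/0.40) | 1.42 to 4.41 | 1.10 to 5.69 | not non-inferior |
| OR 0.5 (= 1/2.0) | 0.28 to 0.88 | 0.22 to 1.14 | non-inferior; superior only at the smaller SE |

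Break-points:
- OR 0.40 has an upper limit below 1 whenever SE < −ln(0.40)/1.96 = 0.467.
- OR 0.5 has an upper limit below 1 whenever SE < ln(2)/1.96 = 0.354.
- An estimate of 2.0 or 2.5 already exceeds 1.6, so its upper limit does so at any SE.

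**Long-run behaviour, SE 0.25 / 0.35 / 0.45 (assumed, bracketing the range above)**

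P(upper < 1.6) = Φ[(ln 1.6 − ln OR)/SE − 1.96].

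- Odds of a worse grade, true OR 1.6 (at the margin): Φ(−1.96) = 0.025 at every SE. The rule is valid.
- Odds of a better grade, true OR 1/1.6 = 0.625 (the same margin inverted): 0.96 / 0.77 / 0.55. A lens at the limit of acceptability usually passes.
- Odds of a better grade, true OR 0.5: the rule declares superiority, Φ[(−ln 0.5)/SE − 1.96], with probability 0.79 / 0.51 / 0.34.

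**If the lower limit of sentence 1 is taken literally**

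That sentence gives no inequality, so both are tried.

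- Lower limit < 1.6: a lens at the worse-grade margin passes Φ(1.96) = 97.5% of the time.
- Lower limit > 1.6: two identical lenses (OR 1) pass at most 0.1% of the time, against 47% / 27% / 18% under upper limit < 1.6.

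Neither is a usable non-inferiority test.

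**The case against.** The strongest reply is that only one decision rule is actually written. The sentence about lower limits contains no inequality and no outcome. The two sentences that draw conclusions agree with each other and both name the upper limit. The direction can then be inferred: if an interval wholly below 1 makes the Test lens superior, values below 1 must favour Test, and with 5 as the best grade that means the odds of a worse grade. The 1.6 margin fits. On this view there is a one-word slip, and the reversal appears only if someone codes the model for better grades and still applies the rule without noticing. Further, fit is one of two co-primary hypotheses, so passing it does not by itself carry the study; and Appendix D and part of Section 14.2 are redacted and might bear on the ordering.

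Much of this stands. The worse-grade reading is the only coherent one and probably the intended one, and the reversal is conditional on the other coding. What does not follow is that the text can be left alone. The direction is inferred from a paragraph that contradicts itself, and Section 14.10 makes that text the governing specification. The redactions could supply the direction, but they cannot reconcile three visible sentences.

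**Conclusion.** The point holds and must be fixed. The conflict between the lower and upper limit is certain from the text. The missing direction is certain as far as the visible text goes.

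Read as the odds of a worse grade with the upper limit governing, the rule is sound, with a 2.5% pass rate at the margin. Coded for better grades, it reverses: a Test lens at the inverted margin of 0.625 passes with probability about 0.55 to 0.96, and a lens estimated at 0.40 is called superior. Those probabilities and the interval widths rest on assumed SEs. The direction of the reversal does not.

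**What to change.** In Sections 2.3 and 14.5, define the odds ratio as the cumulative odds of a lower (worse) fit grade, Test versus Control, and state the category ordering to be used in the model. In Section 14.5, change lower limits to upper limits in the comparison sentence. The rule is then: non-inferior if the upper 95% limit is below 1.6, superior if it is below 1.

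An equivalent alternative is to define the odds ratio for a higher (better) grade and restate both criteria on the lower limit: above 1/1.6 = 0.625 for non-inferiority and above 1 for superiority. Either form works; only one should appear.

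The cost is one or two sentences of wording, with no new data and no extra analysis. The change should be made before the lens codes are unmasked.
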